1. OBJECTIVES

1.1 Study Design

This is a prospective, multicenter, randomized phase II trial of prophylactic obinutuzumab vs. placebo for prevention of chronic Graft vs. Host Disease (cGVHD) after Hematopoietic Cell Transplantation (HCT). A single dose of obinutuzumab or placebo will be administered prophylactically at 3, 6, 9 and 12 months after HCT. Clinical and immunological endpoints are measured sequentially. 200 subjects will be randomized and analyzed in a modified intention-to-treat fashion.

1.2 Primary Objectives

The primary objective is to determine the effect of obinutuzumab prophylaxis on the incidence of corticosteroid-requiring cGVHD after allogeneic HCT. The primary endpoint of this phase II trial is the rate of corticosteroid-requiring cGVHD one year after HCT.

1.3 Secondary Objectives

Secondary objectives are to determine the overall rate of cGVHD after HCT, the rate of NIH moderate-severe cGVHD after HCT, the cumulative incidence of non-relapse mortality and relapse, adverse hematologic events and infections, immunosuppression-free survival (IFS) at 1 and 2 years from transplantation, progression-free and overall survival at 1 and 2 years from transplantation, and immunologic correlates of B cell depletion.

2. BACKGROUND

2.1 Chronic GVHD and B Cells

cGVHD involves inflammatory T- and B-cell responses against allogeneic and autologous antigens and is the most important late complication of allogeneic HCT.¹ With the increasing use of mobilized peripheral blood progenitor cells, and a gradual reduction in early HCT-related mortality,² a steady increase in the incidence of cGVHD has occurred. As a result, cGVHD is the leading cause of late morbidity, impaired quality of life, and mortality after allogeneic HCT.¹;3;4

The mainstay of treatment of cGVHD is systemic corticosteroids, which are associated with incomplete responses and considerable toxicity. Aside from corticosteroids, there are no standards for the treatment of cGVHD, and management of these patients is challenging. There is a desperate need for effective therapeutics in cGVHD, but a preventative approach would be more fruitful. Graft manipulation (through *in vivo* or *ex vivo* T cell depletion or CD34⁺ selection) can prevent cGVHD,^{5;6} but graft manipulation has not been associated with an improvement in overall survival due to excess mortality associated with opportunistic infections and possibly relapse. Allogeneic tolerance induction with post-HCT cyclophosphamide may prevent cGVHD, but long-term outcomes have not been compared with traditional GVHD prevention strategies.⁷

Based on our initial association between the development of anti-H-Y antibodies in sex-mismatched HCT and the occurence of cGVHD,⁸ we and other groups have reported on the use of B cell depletion with rituximab as therapy for established cGVHD.^{9;10} Common to all reported studies, rituximab administration is safe with a low incidence of adverse events. The response rate to a 4 week course of therapy in steroid-refractory settings (375 mg/m²/week in most series), has been as high as 83%,¹¹ although response rates in

the 65% range are more commonly reported. ¹⁰ Cutaneous and myofascial disease were the most responsive in most series.

Several novel strategies have been attempted in cGVHD therapy using rituximab. [name] *et al* have performed a pilot study of rituximab in combination with corticosteroids as initial therapy of cGVHD. 35 subjects with new-onset cGVHD that required corticosteroid treatment received rituximab (375 mg/m²/week x 4) in combination with prednisone (1 mg/kg/day). A second course was allowed for incomplete responses. Response, defined as a complete or partial response with a prednisone dose of <0.25 mg/kg/day, was noted in 40% of subjects at 6 and 12 months, suggesting promising but incomplete activity. While there were 6 deaths from cGVHD within 12 months of rituximab therapy, only 2 subjects suffered a relapse of their malignancy. 12

Given the promising activity of rituximab in the treatment of established cGVHD, and reports of cGVHD prevention with peri-HCT B cell depletion, ^{13;14} we explored the role of rituximab as prevention of cGVHD. ¹⁵ In this phase II trial (DFCI 05-377), rituximab (375 mg/m²) was administered at 100 days, 6, 9 and 12 months after HCT (n=65). The cumulative incidence of cGVHD and systemic corticosteroid-requiring cGVHD at 2 years from HCT were 48% and 31% respectively, lower than rates in a concurrent control cohort (60%, p=0.1 and 48.5%, p=0.015, respectively). In related donors, the incidence of cGVHD and corticosteroid-requiring cGVHD at 2 years was 35% and 23%, whereas the corresponding figures in unrelated donors was 59% and 38% (Figures 1, 2). Rituximab was safe, with no severe infusional events and a 2 year cumulative incidence of grade 3-5 infections of 15%. There was no difference in relapse incidence (34% vs. 28%, p=0.79), but treatment-related mortality at 4 years from HCT was significantly lower in treated subjects when compared with controls (5.1% vs. 19.0%, p=0.02), and overall survival was superior at 4 years (71% vs. 56%, p=0.05). In a multivariable regression model, only rituximab use (HR 0.56, 95% CI 0.31-1.00, p=0.048) and high/very high disease risk index (HR 1.90, 95% CI 1.02-3.53, p=0.04) were significantly associated with overall survival.

[figure not shown]

Figure 1 (left): Incidence of cGVHD with rituximab cGVHD prophylaxis, stratified by donor type. Figure 2 (right): 100 Day Landmark Survival Analysis

In a similar experience, [name] and colleagues also tested the role of rituximab as prevention of cGVHD, and reported similar outcomes using a TLI/ATG preparative regimen. ¹⁶ In this experience involving 35 subjects, Rituximab (375 mg/m²) was infused weekly (days +56, 63, 70, 77). The cumulative incidence of cGVHD was 20%, which is lower than the published rates of cGVHD using this regimen. ¹⁷

2.2 Study Agent

Obinutuzumab (also known as RO5072759, GA101, Gazyva) is a humanized glycoengineered type II anti-CD20 monoclonal antibody (mAb). Obinutuzumab was derived by humanization of the parental B-Ly1 mouse antibody and subsequent glycoengineering leading to the following characteristics: high-affinity binding to the CD20 antigen, high antibody-dependent cellular cytotoxicity (ADCC), and antibody-dependent cellular phagocytosis (ADCP); low complement-dependent cytotoxicity (CDC) activity; and high direct cell death induction. These nonclinical features of obinutuzumab may translate into an anti-CD20 monoclonal antibody with superior clinical efficacy compared to other anti-CD20-mAb.

Obinutuzumab is FDA-approved for use in combination with chlorambucil for the treatment of individuals with previously untreated chronic lymphocytic leukemia.

Obinutuzumab will be provided by Roche/Genentech Inc.

2.3 Rationale

[figure not shown]
In both the preliminary experiences of prevention of cGVHD with rituximab, prevention of cGVHD was incomplete. While it is understood that B cells are not entirely responsible for the pathogenesis of cGVHD, it is hypothesized that a more potent anti-B cell agent could be a more effective prophylaxis agent, since it is known that rituximab-unresponsive cGVHD patients have B cells with a CD20^{Lo} phenotype and persistent elevations in BAFF, ¹⁸ rendering them more resistant to apoptosis via activation of the BCR pathway. ¹⁹

We therefore–propose a randomized, placebo-controlled Phase II trial of obinutuzumab. The size and randomized nature of this multicenter study has the potential to change the field of allogeneic HCT, and could result in improved patient outcomes across multiple tumor types, and across all conditioning intensities.

2.4 Correlative Studies Background

While many mHA are likely involved in cGVHD, the F→M HCT model provides a convenient set of known mHA whose antibody responses can be tracked. The [name] lab has identified a series of 9 highly immunogenic minor histocompatibility (mHA) proteins on the Y chromosome (H-Y proteins). Subjects who underwent F→M HCT, were found to have significantly higher levels of anti-H-Y IgG antibodies, which correlated with a higher rate of cGVHD after HCT. As shown in Figure 3, H-Y antibodies are associated with a higher probability of cGVHD but lower levels of relapse, displaying both the GVHD and GVL

Figure 3: Association between anti-H-Y antibodies with cGVHD and protection from relapse

effects of the allo-immune response.⁸ While antibody responses in humans are correlated with cGVHD, it is important to note that in the mouse, deposition of IgG is involved in the pathology of cGVHD.

The DBY-2 peptide (KNDPERLDQQLANLDLNSEK) contains the DBY-2 epitope, frequently recognized in allogeneic F→M antibody responses that occur following HCT. [name] was able to demonstrate the presence of circulating B cells expressing immunoglobulin receptors that specifically bind DBY-2. In a retrospective analysis of 28 subjects undergoing F→M HCT without prior cGVHD, DBY-2-binding B cells were detected in 16 subjects (57%) 6 months after HCT, with appropriate negative controls, including healthy female donors or male donor PBMC incubated with high-titer anti-DBY-2 IgG (Figure 4).²⁰ Importantly, 15 of these 16 developed cGVHD, including 6 who were diagnosed at the time of the anti-DBY-2 analysis. The absolute and relative number of DBY-2-specific B cells was significantly higher 6

months after HCT in patients who developed NIH moderate or severe cGVHD compared with those with NIH mild cGVHD or no cGVHD at all (P = 0.02; Figure 5). It is important to note that none of the patients with detectable anti-DBY-2 B cells yet had detectable circulating anti-DBY-2 IgG, suggesting that the detection of the B cell is a more relevant marker of impending cGVHD than identification of the circulating antibody. If the anti-DBY-2 antibody is pathogenic then it also argues that intervention prior to the elaboration of the anti-DBY-2 antibody may be fruitful in cGVHD prevention. The phenotype of the DBY-2 specific B cells corresponds to the commonly accepted phenotype for naïve or transitional B cells (CD19⁺IgM⁺IgD⁺CD27⁻CD38⁺CD5⁻), which allows more precise identification of the target B cell for further interventional strategies.

[figure not shown]
[figure not shown]

Figure 4 (left): DBY-2-binding B cells are detected in some $F \rightarrow M$ patients after HCT but not in healthy male and female donors (left column). Data for the X chromosome homologue DBX-2 are shown in right column. Data for 1 representative $F \rightarrow M$ HCT patient, 6 months after HCT (top) and for healthy controls (2nd through 4th panels). (Adapted from Sahaf *et al*, 2013).

Figure 5 (below): HY-specific B-cells predict cGVHD severity.

In the study cited above of primary therapy of cGVHD using corticosteroids and rituximab, cGVHD clinical response was predicted by a naïve (CD19+CD38-IgD+CD27-) B cell phenotype (p=0.03).¹² 15 cGVHD subjects underwent had F→M HCT, and 6 (38%) were H-Y IgM positive while 9 (56%) were IgG positive at cGVHD diagnosis. Among 15 F→M HCT recipients with cGVHD treated with rituximab, 11 responded, and both H-Y IgM and IgG became undetectable for at least 6 months following rituximab. In contrast, the 4 F→M subjects who did not respond remained H-Y IgG positive. Moreover, 2 subjects that redeveloped H-Y IgG later had recurrent cGVHD. H-Y antigen-specific B cells depleted after rituximab recovered in 6 of the 11 F→M assayed, suggesting that alternative anti-B cell strategies are required.

In the Stanford trial of primary prevention of cGVHD with rituximab, rituximab administration significantly reduced B cell allogeneic immunity. In 10 F→M recipients enrolled in this trial, there was complete prevention of alloreactive H-Y antibody development, and none of these subjects developed cGVHD. In comparison, among 25 F→M HCT patients who used the same TLI-ATG conditioning regimen but without prophylactic rituximab during this time period, 14 of the 25 (56%) developed H-Y antibodies, with 13 of the 25 (52%) developing cGVHD (p=0.01).¹6 Similarly, in our trial of primary cGVHD prevention with rituximab (DFCI 05-377), of 13 F→M recipients, none developed anti-DBY antibodies between 6 months and 1 year from HCT, whereas 4 of 10 F→M control recipients developed anti-DBY antibodies in the same time period (p=0.02).

In this clinical trial, samples from all $F \rightarrow M$ recipients will be collected and analyzed for the presence of pathogenic alloreactive H-Y antibodies as well as pathogenic anti H-Y B cells. Samples will also be analyzed for non H-Y restricted antibodies (preliminary data not shown).

3. PARTICIPANT SELECTION

3.1 Eligibility Criteria

- 3.1.1 Subjects deemed potentially eligible by their treating physicians will be screened for enrollment after d+60 from transplantation
- 3.1.2 Patients who have undergone either ablative or non-myeloablative allogeneic stem cell transplantation are eligible.
- 3.1.3 Peripheral blood stem cells must have been used as the stem cell source.
- 3.1.4 Patients must have received transplantation from donors (both related and unrelated) who are identical at 8 HLA loci (A, B, C and DRβ1), or mismatched at no more than 1 locus (7/8). Among related donors, HLA C typing is not required (6/6 HLA matches). Class I typing is to be performed by PCR-SSP techniques and CDC techniques. Class II typing is performed by PCR-RFLP +/- PCR-SSP techniques.
- 3.1.5 No evidence of relapsed or residual malignancy within 30 days of trial entry. All patients must undergo appropriate staging for their malignancy (i.e. bone marrow aspiration for the leukemias and PET-CT scanning for the lymphomas). Evidence of a persistent cytogenetic abnormality will constitute evidence of residual or relapsed disease in the leukemias, where present. Individuals with CLL are eligible if there is no more than 20% residual leukemia in the bone marrow at the time of study entry.
- 3.1.6 Patients who have undergone a non-myeloablative stem cell transplant must have > 80% donor hematopoiesis within 30 days of study enrollment. Chimerism within 30 days of study entry must be greater than, equal to, or no more than 5% less than the chimerism measured at approximately day+30 (if performed).
- 3.1.7 Age ≥ 18.0
- 3.1.8 ECOG performance status ≤ 2 (Karnofsky $\geq 60\%$) (See Appendix A)
- 3.1.9 Participants must have normal marrow function as defined by:

 $\begin{array}{lll} - & WBC & & \geq 2,500/\mu L \\ - & Absolute \ Neutrophil \ Count & \geq 1,000/\mu L \\ - & Platelets & \geq 50,000/\mu L \end{array}$

3.1.10 Ability to understand and the willingness to sign a written informed consent document.

3.1.11 The effects of obinutuzumab on the developing human fetus are unknown. For this reason, women of child-bearing potential and men must agree to use adequate contraception (hormonal or barrier method of birth control; abstinence) prior to study entry and for the duration of study participation. Should a woman become pregnant or suspect she is pregnant while she or her partner is participating in this study, she should inform her treating physician immediately. Men treated or enrolled on this protocol must also agree to use adequate contraception prior to the study, for the duration of study participation, and 4 months after completion of obinutuzumab administration.

3.2 Exclusion Criteria

- 3.2.1 Allogeneic stem cell transplantation using a single or multiple umbilical cord blood units or using bone marrow.
- 3.2.2 Allogeneic stem cell transplantation using in vivo or ex vivo T cell depletion, either by cell manipulation or with T cell depleting antibodies (Any anti-thymocyte globulin preparation or alemtuzumab given within 30 days of transplantation)
- 3.2.3 Participation in a clinical trial evaluating another preventative strategy for chronic GVHD, or ongoing participation in a clinical trial for therapy of acute GVHD. Prior completion of experimental therapy for acute GVHD is permissible if the experimental agent was used > 30 days prior to enrollment.
- 3.2.4 Any evidence of ongoing gastrointestinal or hepatic acute GVHD, or evidence of greater than ongoing Stage I cutaneous acute GVHD. Ongoing, tapering therapy for resolved acute GVHD is permissible.
- 3.2.5 Any evidence of prior active or resolved chronic GVHD.
- 3.2.6 Any evidence of cGVHD or late aGVHD between enrollment and first dose of obinutuzumab.
- 3.2.7 History of severe allergic reaction to obinutuzumab
- 3.2.8 No Donor Lymphocyte Infusion (DLI) prior to day 100, and no plans for a DLI in the upcoming 30 days.
- 3.2.9 Evidence of any active uncontrolled infection (bacterial, viral or fungal) or evidence of natural exposure to Hepatitis B, Hepatitis C or HIV. Evidence of Hepatitis B exposure includes the presence of Hepatitis B surface antigenemia, a positive serological test for Hepatitis B core antibody or nucleic acid testing (NAT testing) that is positive for Hepatitis B. Vaccination to Hepatitis B is not an exclusion criteria. Testing done in the pre-transplant setting is sufficient to rule out infection.
- 3.2.10 Pregnancy or lactation. Negative pregnancy test is required within the screening window for women of child bearing potential.
- 3.2.11 Active use of any other investigational agents.

3.3 Inclusion of Women and Minorities

Both men and women of all races and ethnic groups are eligible for this trial.

4. REGISTRATION PROCEDURES

4.1 General Guidelines for DF/HCC and DF/PCC Institutions

Institutions will register eligible participants in the Clinical Trials Management System (CTMS) OnCore. Registrations must occur prior to the initiation of protocol therapy. Any participant not registered to the protocol before protocol therapy begins will be considered ineligible and registration will be denied.

An investigator will confirm eligibility criteria and a member of the study team will complete the protocol-specific eligibility checklist.

Following registration, participants may begin protocol therapy. Issues that would cause treatment delays should be discussed with the Overall Principal Investigator (PI). If a participant does not receive protocol therapy following registration, the participant's registration on the study must be canceled. Registration cancellations must be made in OnCore as soon as possible.

4.2 Registration Process for DF/HCC and DF/PCC Institutions

DF/HCC Standard Operating Procedure for Human Subject Research Titled *Subject Protocol Registration* (SOP #: REGIST-101) must be followed.

4.3 General Guidelines for Other Investigative Sites

Eligible participants will be entered on study centrally at the DFCI by the Study Coordinator.

Following registration, participants should begin protocol therapy within 14 days. Issues that would cause treatment delays should be discussed with the Overall PI. If a participant does not receive protocol therapy following registration, the participant's registration on the study must be canceled. The Study Coordinator should be notified of cancellations as soon as possible.

4.4 Registration Process for Other Investigative Sites

For information regarding the registration process, please refer to section 3.7 of the DSMP located in appendix D.

5. TREATMENT PLAN

5.1 Stem Cell Transplantation

All subjects will undergo allogeneic stem cell transplantation according to locally approved clinical trials or treatment plans. No specific conditioning regimen or GVHD prophylaxis regimen is mandated. The stem cell source must have been peripheral blood stem cells. No *in vitro* or *in vivo* T cell depletion is permitted. Participation in a clinical trial evaluating novel approaches to acute GVHD prophylaxis is not

allowed, but participation in a trial evaluating novel agents for therapy of acute GVHD is allowed, as long as the experimental agent was discontinued > 30 days prior to trial entry.

5.2 Trial Screening and Entry

Subjects deemed potentially eligible by their treating physicians will be screened for enrollment after day +60 from transplantation. Once screened, deemed eligible and registered, the subject will be randomized in a 1:1 to the active treatment (obinutuzumab) or placebo arm. Stratification will be by center, conditioning intensity and donor type, using a permuted block algorithm within strata. Blinding will be maintained at the level of the Research Pharmacy.

5.3 Treatment Regimen

Obinutuzumab or placebo will be administered at a dose of 1000 mg, intravenously, at 3, 6, 9 and 12 months from transplantation. The first dose is administered at day +90 (+/- 10 days), followed by doses at days +180 (+/- 10 days), 270 (+/- 10 days) and +365 (+/- 10 days).

Premedication with histamine blockers and acetaminophen will be provided (see Section 5.5 below), but corticosteroids at the time of obinutuzumab infusion are not permitted. Placebo will be administered with the same premedications and precautions.

No dose modifications are permitted, although doses may be skipped based on unresolved toxicity (see Section 6: Dosing Delays/Dose Modifications). If a dose is missed, the investigator may choose to continue with protocol-specified treatments within the next dosing time period.

5.4 Pre-Treatment Criteria for Doses 1, 2, 3 and 4

There are no criteria for treatment at dose 1. Dose 1 will be administered at the discretion of the provider.

Criteria for treatment at doses 2, 3 and 4 are:

 $\begin{array}{lll} - & WBC & & \geq 2,500/\mu L \\ - & Absolute \ Neutrophil \ Count & \geq 1,000/\mu L \\ - & Platelets & \geq 50,000/\mu L \end{array}$

The occurrence of acute GVHD prior to doses 2, 3, 4 is allowed as long as all GVHD symptoms are resolved to Gr 0 for hepatic and gastrointestinal disease and Gr I for cutaneous disease, per section 3.2.43.2.4

5.5 Agent Administration

Initial Dose

Research subjects should be premedicated with Acetaminophen (650 - 1000 mg oral) and Diphenhydramine (25-50 mg intravenous).

Obinutuzumab or placebo is administered initially at 50 mg/h. In the absence of infusional reactions, the rate can be increased in increments of 50 mg/h every 30 minutes to a maximum of 400 mg/h. With this schedule, a 1000 mg dose of Obinutuzumab will be infused over 4.25 hours. See Table 1.

Second and Subsequent Doses

Doses and schedules are adapted from Phase I and Phase II studies in non-CLL patient populations. 21-24

Research subjects should be premedicated with Acetaminophen (650 - 1000 mg, oral) and Diphenhydramine (25-50 mg, intravenous).

In the absence of severe infusional reactions with the initial dose, Obinutuzumab can be administered initially at 100 mg/h. In the absence of infusional reactions, the rate can be increased in increments of 100 mg/h every 30 minutes to a maximum of 400 mg/h. With this schedule, a 1000 mg dose of Obinutuzumab will be infused over 3.25 hours. See Table 1.

Placebo will administered at the same rate with the same pre-medications as obinutuzumab.

l'able 1. Adminis	tration of Obinutuz	rumab		
1st Dose				
Rate	Duration	Dose Delivered	Total Time	Cumulative Dose
50 mg/hr	30 minutes	25 mg	0.5 hours	25 mg
100 mg/hr	30 minutes	50 mg	1 hour	75 mg
150 mg/hr	30 minutes	75 mg	1.5 hours	150 mg
200 mg/hr	30 minutes	100 mg	2 hours	250 mg
250 mg/hr	30 minutes	125 mg	2.5 hours	375 mg
300 mg/hr	30 minutes	150 mg	3 hours	525 mg
350 mg/hr	30 minutes	175 mg	3.5 hours	700 mg
400 mg/hr	45 minutes	300 mg	4.25 hours	1000 mg
2 1 16 1	4 D			
2nd and Subs				
Rate	Duration	Dose Delivered	Total Time	Cumulative Dose
100 mg/hr	30 minutes	50 mg	0.5 hour	50 mg
200 mg/hr	30 minutes	100 mg	1 hours	150 mg
300 mg/hr	30 minutes	150 mg	1.5 hours	300 mg
400 mg/hr	1.75 hours	700 mg	3.25 hours	1000 mg

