5.6 Management of Infusion Reactions

Infusion reactions are noted in the presence of high tumor burden in the treatment, and as a result are more frequent in the treatment of CLL in comparison with NHL. Stem cell transplant recipients are leukopenic and are anticipated to have an even lower likelihood of infusion reactions than B cell malignancy patients.

Infusion reactions should be managed according to the grade of the reaction. For Grade 4 reactions, the infusion must be stopped and permanently discontinued. For Grade 3 reactions, the infusion should be temporarily interrupted and appropriate medication administered to treat the symptoms. For Grade 1–2 reactions, the infusion should be slowed down and symptoms treated as appropriate. Upon resolution of symptoms, infusion can be restarted, except following Grade 4 IRR, at no more than half the previous rate and, if the patient does not experience the same adverse event with the same severity, infusion rate escalation may resume at the increments and intervals as appropriate for the treatment dose.

For infusion reactions, additional doses of H₁- and H₂-blocking antihistamine agents are administered. Corticosteroids may be administered but only for Grade 3 or 4 reactions when deemed necessary by the treating physician.

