7.1 Expected Toxicities of Obinutuzumab

7.1.1 Infusion-Related Reactions

Infusion-related reactions (IRRs) were observed consistently in all obinutuzumab trials; the highest incidence of IRR was at the first infusion with the incidence decreasing rapidly with subsequent infusions. The incidence of IRR observed with combination therapy (FC and CHOP) appears similar to that observed with monotherapy. Furthermore, the incidence of IRR appears to be higher in CLL compared to NHL patients and higher in obinutuzumab- compared to rituximab-exposed patients based on evidence from studies BO21003 and BO21999. There is no clear relationship between obinutuzumab dose and the incidence of IRR based on data from study GAO4768g. In Stage 2 of the pivotal Phase III study, BO21004/CLL 11, investigating GClb vs RClb in patients with CLL, the incidence of IRR, Grade 3/4 IRR and IRR leading to discontinuation was higher in GClb arm compared to RClb. This study investigated several measures to minimize the risk of IRRs including: use of corticosteroids, withdrawal of antihypertensive treatments, slow infusion, and split dosing and the evidence suggests that these risk minimization measures decreased the risk of IRRs (all grades); however, the impact on the incidence of Grade 3-4 events and treatment discontinuations due to IRR was limited.

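### The condition for the faster infusion at doses 2 to 4 checks only dose 1, so a patient whose first Grade 3 infusion reaction comes at dose 2 or 3 still qualifies for the same faster schedule at the next dose

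*Combined protocol and SAP*

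**What the plan says.** Section 5.5 gives two infusion schedules. The first dose starts at 50 mg/h and rises by 50 mg/h every half hour. Doses 2, 3 and 4 share one heading and one condition: "In the absence of severe infusional reactions with the initial dose, Obinutuzumab can be administered initially at 100 mg/h". They then rise by 100 mg/h every half hour, with the same 400 mg/h ceiling. Section 8.1.8 repeats the condition. The second block of Table 1 sets out the faster schedule and carries no condition. Placebo follows suit: "Placebo will administered at the same rate with the same pre-medications as obinutuzumab".

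Section 5.6 deals with the infusion in which a reaction occurs. Grade 3 means interrupt and treat, and Grade 4 means stop permanently. After symptoms resolve, "infusion can be restarted, except following Grade 4 IRR, at no more than half the previous rate".

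On steroids, section 5.3 says "corticosteroids at the time of obinutuzumab infusion are not permitted", while section 5.6 allows them as treatment: "Corticosteroids may be administered but only for Grade 3 or 4 reactions when deemed necessary by the treating physician".

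On expected frequency, section 7.1.1 says "the highest incidence of IRR was at the first infusion with the incidence decreasing rapidly with subsequent infusions".

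**The concern.** The protocol's own logic is that a severe reaction should cost the patient the faster schedule. The condition applies that logic to dose 1 only, although it governs three later doses. For a patient whose first Grade 3 reaction is at dose 2 or 3, it looks at the wrong dose. Dose 2 is also the first exposure to the 100 mg/h start, so a reaction related to rate could first appear there, and the written rule would take no account of it.

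Infusion rate is one of few preventive measures here. With steroid premedication barred, what remains is acetaminophen and diphenhydramine. Two smaller gaps sit alongside: section 5.5 does not tie 'severe' to the grades used in section 5.6, and the text never says which schedule applies when the condition fails. The 50 mg/h schedule is only implied.

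At stake is the safety of a small number of later infusions. The rate plays no part in the primary endpoint or its analysis in section 12.6.

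**Working it through.** **1. Reproduce Table 1.** Cumulative dose = sum of rate × time, in 0.5 h steps.

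| Time | First-dose schedule | Doses 2 to 4 schedule |
|---|---|---|
| 0.5 h | 25 mg | 50 mg |
| 1.0 h | 25 + 50 = 75 mg | 50 + 100 = 150 mg |
| 1.5 h | 75 + 75 = 150 mg | 150 + 150 = 300 mg |
| 400 mg/h begins | 3.5 h | 1.5 h |
| 1000 mg complete | 4.25 h | 3.25 h |

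These match the protocol. The contrast at 1.5 h is 300/150 = 2. It arises only if the physician chooses the faster start and no reaction occurs on the way up, because section 5.5 makes each increase depend on the absence of reactions.

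**2. Look for another rule that covers the gap.**
- Section 5.4: criteria for doses 2 to 4 are blood counts and GVHD status. Infusion reactions are not mentioned.
- Section 5.6: acts within the infusion in which the reaction occurs. No starting rate for the next dose.
- Sections 5.3 and 6: no dose modification, skipping for unresolved toxicity, and delay within the window. Nothing on rate.
- Section 5.9: removal for unacceptable adverse events or on the investigator's judgment. No reaction grade is named, and it does not guide a patient who continues.

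None sets the rate.

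**3. Who is exposed.** A first Grade 3 reaction at dose 2 leaves doses 3 and 4 uncovered; at dose 3 it leaves dose 4. Grade 4 is outside the gap, because section 5.6 ends the infusion permanently.

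**4. How many.** The documents give no obinutuzumab reaction rate after transplant. Assumption: borrow the rituximab pilot in section 2.1, with 0 severe infusion reactions in 65 patients.
- Exact one-sided 95% upper bound: 1 − 0.05^(1/65) = 0.045.
- Active arm: 200/2 = 100 patients, 100 × 4 = 400 planned infusions.
- Patients with a severe reaction: 0 to 100 × 0.045 = 4.5.
- If all of these first reacted at dose 2: 4.5 × 2 = 9 of 400 infusions (2.3%).
- If all at dose 3: 4.5 × 1 = 4.5 of 400 (1.1%).

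These are ceilings. They take the upper bound on an observed zero and place every event at a later dose, whereas section 7.1.1 puts the highest incidence at the first infusion.

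**The case against.** The case for leaving the text alone has several sound parts.

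- **Discretion.** The condition says the faster start can be used, not that it must be. The physician may start slower, stop treatment under section 5.9, or skip a dose for unresolved toxicity. This stands and keeps the point small. But nothing asks for the slower start, and staff working from Table 1 would find only the faster block for doses 2 to 4.
- **Rarity.** Section 5.6 expects transplant recipients to react less often than patients with B-cell malignancy, and section 7.1.1 expects a rapid fall after dose 1. This stands. Section 7.1.1 also says reactions are "higher in obinutuzumab- compared to rituximab-exposed patients", but that comparison comes from other obinutuzumab studies and the passage gives no multiplier, so it does not justify scaling the ceilings up by any particular factor.
- **Limited benefit.** Section 7.1.1 reports that measures including slow infusion lowered reactions of all grades, but "the impact on the incidence of Grade 3-4 events and treatment discontinuations due to IRR was limited". This also stands. A slower start may do little against a repeat Grade 3 event.
- **Possible intent.** The schedules were adapted from cited studies, so the dose 1 condition may have been deliberate. The documents do not say.

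Two stronger readings are tempting. A reader might infer that the rule speeds up the infusion for someone who has just reacted. It does not: a patient who tolerated dose 1 would normally have had dose 2 on the 100 mg/h schedule already, so the next dose, about three months later, runs at the same rate. The rule fails to require tightening. A reader might also infer a conflict with the half-rate restart in section 5.6. That limit applies within one infusion. Halving 100, 200, 300 and 400 mg/h gives 50, 100, 150 and 200 mg/h, which is below the 100 mg/h start only for a reaction at the first step.

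**Conclusion.** The gap holds on the text. Sections 5.5 and 8.1.8 look back only to dose 1, and no other section sets a starting rate after a first Grade 3 reaction at dose 2 or 3. For such a patient the permitted difference is a factor of two in dose delivered by 1.5 h.

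The size is small: no affected infusions if the pilot's zero carries over, and at most about 9 of 400 under the borrowed rituximab bound, probably far fewer. This rests on two assumptions: that 'severe' means Grade 3, and that the rituximab pilot is a usable guide to obinutuzumab in this setting. It is a minor safety correction, worth making because it costs almost nothing. The documents do not support calling it a significant hazard, and the primary analysis is unaffected.

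**What to change.** At the next amendment:

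1. In sections 5.5 and 8.1.8, replace the reference to the initial dose with *with any previous dose (Grade 3)*.
2. Add after it: *After a Grade 3 reaction at any previous dose, if treatment continues, use the first-dose schedule (50 mg/h start). Grade 4 reactions are handled under section 5.6.*
3. Add a matching footnote to the second block of Table 1, which at present has no condition.
4. State that the rule applies to obinutuzumab and placebo alike.

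The Grade 4 clause matters. A rule that sent Grade 3 or higher to the slower schedule would imply re-dosing after a Grade 4 reaction, against section 5.6. The phrase *if treatment continues* leaves the section 5.9 decision with the investigator.

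Cost: a few lines of text, with no new visits, tests or patients. Each affected infusion takes 4.25 − 3.25 = 1 h longer.
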